8.6 Demographics and Baseline Characteristics

Demographic and baseline characteristics will be summarized with descriptive statistics by the treatment group for the safety population, the ITT population, and the mITT population.

8.7 Prior Therapies

Prior therapies for drugs will be coded using the World Health Organization (WHO) Drug Dictionary. Patients who received prior therapy(ies) will be listed for the safety population and the ITT population.

8.8 Concomitant Therapies

Concomitant therapies for drugs will be coded using the WHO Drug Dictionary. Patients who received concomitant therapy(ies) will be listed for the safety population and the ITT population.

8.9 Efficacy Analyses

8.9.1 Primary Efficacy Endpoint

The primary efficacy endpoint is the CTL induction rate within 12 weeks after initial dose, defined as the proportion of patients who show in vitro CTL induction to at least any of the 5 antigens (DEPDC1, MPHOSPH1, URLC10, CDCA1, and KOC1). The CTL induction is defined as the increase in the CTL activity at any point after baseline (eg, from [-] to [2+], from [+] to [2+]). Baseline is defined as the CTL measurement taken prior to dosing on the date of the first dose.

8.9.2 Secondary Efficacy Endpoints

The secondary efficacy endpoints include the following variables:

- CTL induction rate within 1 year after initial dose, defined as the proportion of patients who show in vitro CTL induction to at least any one of the 5 antigens.
- Response rate (RR), defined as the proportion of patients who are assessed as CR or PR by using RECIST version 1.1 and irRC, respectively.
- Disease control rate (DCR), defined as the proportion of patients who are assessed as CR, PR, or SD by using RECIST version 1.1 and irRC, respectively.
- Any response rate in image analysis such as tumor cavitation, defined as the proportion of patients who show any tumor change in image analysis (eg, tumor cavitation).
- PFS, defined as the time interval from the date of enrollment to the date of progression (in order of the following priority; PD by central review based on RECIST version 1.1, withdrawal due to aggravation of the target disease, or progression of the target disease by the investigator in Vital Status Follow-up Form) or death due to any cause, whichever occurs first.
- OS, defined as the time interval from the date of enrollment to the date of death due to any cause or the date of last follow-up.
- Change in QOL, defined as change from baseline in the global health status, the function scales, and the symptom scales on the EORTC QLQ-C30 questionnaire, and the index value and the EQ VAS on the EQ-5D-5L questionnaire, respectively. Baseline is defined as the value obtained at Visit 1 (pre-dose).

8.9.3 Analyses of Efficacy Endpoints

8.9.3.1 CTL Induction Rate for the S-588410 Group

For the mITT population, CTL induction rate and the associated 90% CI will be estimated by visit. As the primary analysis, one-sided binomial test where the null hypothesis is that the CTL induction rate within 12 weeks is equal to 0.5 or less will be performed at a significance level of 0.05. The 90% CI will then be calculated by using the Clopper-Pearson method.

The number of antigens with CTL induction will be tabulated by visit.

As a sensitivity analysis, the primary efficacy endpoint will be analyzed using the PPS.

8.9.3.2 Tumor Response

- Response rate and disease control rate using RECIST version 1.1 and irRC:
For the ITT population, the RR and the DCR using RECIST version 1.1 and irRC will be determined, and the associated 90% CIs will be calculated for the S-588410 Group and the Observation Group, respectively.
- Any response rate in image analysis such as tumor cavitation:
For the ITT population, the response rate in image analysis will be determined, and the associated 90% CI will be calculated for the S-588410 Group and the Observation Group, respectively.

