3.2 Rationale for Study Design

3.2.1 Rationale for the patient population

The patient population eligible for this study was selected based on the following reasons:

- As stated in the Food and Drug Administration (FDA) Guidance for Industry “Clinical considerations for therapeutic cancer vaccines October 2011” [14], patients with no evidence of residual diseases or minimal burden of disease may provide adequate time for the cancer vaccine to elicit a detectable immune response.
- Platinum-containing chemotherapy is recommended as the standard first-line chemotherapy in all regions of US and Europe, and Japan (GC or MVAC as the main choice) [3, 4, 5].
- For the majority of the patients, the disease will continue to progress even after completion of the first-line chemotherapy, as evidenced by the poor 5-year survival data.
- There are currently no treatments approved for maintenance therapy following first-line platinum containing chemotherapy in this patient population.
- Maintenance therapy (in patients after first-line chemotherapy including patients whose disease responds or remain stable) has been reported in several clinical studies [11, 12, 13].

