4.2 Inclusion Criteria

Patients who fulfill all of the following criteria assessed by the end of screening period will be included in the study.

1. Patients with advanced and/or metastatic bladder cancer (including urothelial cancer of renal pelvis, ureters, and urethra) who have CR, PR, or SD based on the Response Evaluation Criteria in Solid Tumors (RECIST) version 1.1 at the end of at least 4 cycles of first-line platinum-containing systemic chemotherapy.
(Note: Patients who have subsequently received another platinum-containing chemotherapy due to intolerance* of first-line platinum-containing chemotherapy are eligible if the total number of cycles of platinum-containing regimens reached 4 cycles or more. The patients had no PD at the time of change of platinum-containing chemotherapy. *: any non-hematologic toxicity with grade 3 or higher, or hematologic toxicity with grade 4, according to Common Terminology Criteria for Adverse Events [CTCAE] version 4.03.)
2. Patients who are male or female aged ≥ 20 years at the time of informed consent.
3. Patients with the ECOG PS 0 or 1 at enrollment.
4. Patients who have a lymphocyte count accounting for 15% or higher of the total white blood cell count within 28 days before enrollment.
5. Patients who are willing and able to provide formalin-fixed and paraffin-embedded bladder cancer tissues for antigen expression measurement.
6. Patients who provide a personally signed and dated informed consent document for participation in the study.

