7.3.2 Tumor Evaluation

In both the S-588410 and the Observation Groups, a computed tomography (CT) scan or an magnetic resonance imaging (MRI) scan will be performed in accordance with a separate imaging manual throughout the study at the time points specified in the schedule of events ([Appendix 1](#) and [Appendix 2](#)). All original images or those copies will be submitted to the central imaging for central review (see also section [9.1](#)).

Tumor evaluation, based on RECIST Version 1.1 and immune-related response criteria (irRC), will be performed by central review with the following categories: CR, PR, SD, and PD for the RECIST; irCR, irPR, irSD, and irPD for the irRC. A status of stable disease will only be assigned if the evaluation is unchanged for at least 6 weeks after enrollment. A status of CR or PR will only be assigned if the evaluation is unchanged for at least 4 weeks.

Tumor evaluation will also be assessed for any response in image analysis such as tumor cavitation based on the criteria stipulated in the separated manual by central review (see also section [9.1](#)).

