8.3 Analysis Populations

The modified intention-to-treat (mITT) population will be the primary population for the primary efficacy endpoint. The intention-to-treat (ITT) population will be the analysis

population for secondary efficacy endpoints. The per-protocol set (PPS) will be used for sensitivity analyses.

- **ITT population** includes all enrolled patients.
- **mITT population** includes all patients who are included in the ITT population and who have a CTL activity measurement at baseline and at least 1 CTL activity measurement after the initiation of study drug administration. Patients whose CTL activities are not available to all of 5 antigens at baseline or are already extremely strong (3+) to all of 5 antigens at baseline are excluded from the mITT population.
- **Per-protocol set (PPS)** includes all patients who are included in the mITT population and do not meet any of the following conditions:
 - Patients with any protocol inclusion or exclusion violations
 - Patients who have insufficient treatment compliance of study drug
 - Patients with violations of restrictions for concomitant drug and concomitant therapy.
- **Safety population** includes all enrolled patients in the S-588410 Group who receive at least 1 actual dose of S-588410 and all patients enrolled in the Observation Group.

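### Response rate is computed in all enrolled patients although patients with no disease left after chemotherapy are eligible, so it does not estimate response among patients who can respond

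*Protocol*

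**What the plan says.** Protocol 4.2, criterion 1, admits patients "who have CR, PR, or SD based on the Response Evaluation Criteria in Solid Tumors (RECIST) version 1.1" after at least four cycles of first-line platinum chemotherapy. Nothing in 4.2 or 4.3 asks for measurable or residual disease. Section 3.2.1 shows that this is deliberate: it cites guidance that "patients with no evidence of residual diseases or minimal burden of disease may provide adequate time for the cancer vaccine to elicit a detectable immune" reaction.

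Section 8.9.2 defines RR as "the proportion of patients who are assessed as CR or PR by using RECIST version 1.1 and irRC, respectively". Section 8.9.3.2 gives the population: "For the ITT population, the RR and the DCR using RECIST version 1.1 and irRC will be determined", with 90% CIs for each group. Section 8.3 states that the ITT population "includes all enrolled patients".

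Section 7.3.2 lists the central-review categories as "CR, PR, SD, and PD for the RECIST; irCR, irPR, irSD, and irPD for the irRC". It adds: "A status of CR or PR will only be assigned if the evaluation is unchanged for at least 4 weeks". Table 7-3 places the screening tumour evaluation within 28 days before enrolment, so it follows the chemotherapy.

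**The concern.** RR serves the secondary objective of estimating antitumour effect. For that purpose it should reflect tumour response that arises after enrolment, among patients who have tumour to respond.

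A patient with no disease on the enrolment scan fits neither part of that. If the patient stays disease-free and is called CR, RR counts a response that chemotherapy produced. If the patient is not called CR, the denominator holds someone for whom response is impossible. The condition in 7.3.2 that a CR or PR be unchanged for four weeks does not settle the matter, because a maintained entry CR satisfies it. The observed-case rule in 8.4 does not remove these patients either, since they are scanned like everyone else.

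At stake is the meaning of the reported RR, under both RECIST 1.1 and irRC and in both groups.

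**Working it through.** **The plan's own figure.** The protocol gives no design figure for RR. Its only sample size, in 8.2, is for the CTL endpoint: 35 patients, and 35/0.85 = 41.2, rounded up to 42. I use N = 42, which is the S-588410 Group target and the Observation Group maximum.

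**Inputs.**
- RR = (patients assessed CR or PR)/(all enrolled): 8.9.2, 8.9.3.2 and 8.3.
- c = share of enrolled patients with no disease on the enrolment scan. Not in the protocol; assumed 10%, 20% and 30%.
- m = share of those patients who keep their CR. Not in the protocol; 100% is the upper bound.
- q = response rate among patients with disease on the enrolment scan, which is the quantity wanted.
- 90% intervals are Clopper-Pearson. The protocol names that method for the CTL rate; using it for RR is my assumption.

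**Formulas.**
- Maintained entry CR counted as CR: RR = q(1 - c) + mc, at most q(1 - c) + c.
- Maintained entry CR not counted: RR = q(1 - c).
- Denominator limited to patients with disease at enrolment: RR = q.

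With m = 1 the two ITT readings differ by exactly c. The uncounted reading equals q only if c = 0 (or q = 0). The counted reading with m = 1 exceeds q by c(1 - q), which is zero only if c = 0 (or q = 1).

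**No on-study response (q = 0), all entry CRs maintained (m = 1).**

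| c | In CR at entry | ITT RR if counted (90% CI) | RR in patients with disease (upper 90% limit) |
|---|---|---|---|
| 10% | 4 | 4/42 = 9.5% (3.3-20.5) | 0/38 = 0% (7.6%) |
| 20% | 8 | 8/42 = 19.0% (9.8-31.8) | 0/34 = 0% (8.4%) |
| 30% | 13 | 13/42 = 31.0% (19.4-44.6) | 0/29 = 0% (9.8%) |

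If only half keep their CR, the spurious part is mc: 0.10 x 0.5 = 5% up to 0.30 x 0.5 = 15%.

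**Response rate near 20% among patients with disease.**
- c = 20%: 7 of 34 respond (20.6%). ITT RR is (7 + 8)/42 = 35.7% if entry CRs count and 7/42 = 16.7% if they do not.
- c = 30%: 6 of 29 respond (20.7%). ITT RR is (6 + 13)/42 = 45.2% or 6/42 = 14.3%.

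**Patients entering in PR or SD.** Their reference scan is taken after chemotherapy, so a response measured from it needs new shrinkage. They carry no automatic credit and belong in the denominator.

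**The case against.** The best defence is that classification of a lesion-free patient is a detail for the SAP or the imaging manual. That holds for the classification rule, and its absence alone would be no finding. But 8.9.2 and 8.9.3.2 already fix the definition and the all-enrolled denominator, and 8.1 says that the SAP is to follow that section. Whichever classification is chosen later, one of the two distortions follows.

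Other points against the concern stand and limit it:
- RR is secondary and descriptive, with no test, threshold or role in the sample size. DCR, PFS and an image-change rate are also reported, and the introduction describes maintenance as postponing progression.
- Eligibility refers to response at the end of chemotherapy, whereas c refers to the enrolment scan. The two can differ, so c may be smaller than the share admitted in CR.
- Both c and m are assumptions. If entry CRs are not counted, the distortion lowers RR.

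A reader might infer that RR credits chemotherapy responses in general, or cannot be interpreted at all. The protocol does not support that, because only patients disease-free on the enrolment scan are involved. A reader might also infer that a false difference between the HLA-defined groups would enter a comparison. An imbalance in c would indeed shift the two rates apart, but RR is given separately for each group and no between-group test of it is planned. Nor do the documents describe how irRC measures tumour burden, so no separate irRC argument can be built. The point reaches irRC only because the same population applies.

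**Conclusion.** The concern holds for patients with no disease on the enrolment scan. As fixed in the protocol, RR in the ITT population is at most q(1 - c) + c or equals q(1 - c), depending on a rule that the protocol does not state. Neither is in general the response rate among patients who can respond unless c = 0.

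With c assumed at 10-30%, N = 42, no on-study response and all entry CRs maintained, RR would be about 10-31% instead of 0%, and less if some CRs are lost. The direction and the algebra follow from the text. The size rests wholly on the assumed c and m. The flaw is worth correcting, but it is confined to a descriptive secondary estimate. The primary CTL analysis and its sample size are unaffected.

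**What to change.** In 8.9.2 and 8.9.3.2:
- Compute RR (RECIST 1.1 and irRC) and its 90% CI in patients with residual disease, measurable or non-measurable, on the enrolment scan. Restricting to measurable lesions would also drop patients with non-measurable residual disease, who are not the problem.
- Report patients without disease at enrolment separately, as remained disease-free or progressed.
- Keep DCR in the ITT population, shown by CR versus non-CR at entry. A patient who stays disease-free meets the DCR definition whether called CR or SD, so that denominator does not need to change.

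The screening scan is already scheduled and images already go to central review, so the cost is protocol wording and some precision. For example, at c = 20% with 7 responders, the 90% CI is 10.1-35.2% on 34 patients (width 25.1 points), against 8.1-29.0% on 42 (width 20.9 points).

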8.9.3.3 Progression Free Survival

For the ITT population, the PFS will be estimated with the Kaplan-Meier method and the median PFS and the associated 90% CI will be presented for the S-588410 Group and the Observation Group, respectively.

8.9.3.4 Overall survival

For the ITT population, the OS will be estimated with the Kaplan-Meier method and the median OS and the associated 90% CI will be presented for the S-588410 Group and the Observation Group, respectively.

8.9.3.5 QOL

For the ITT population, the change from baseline in the global health status, the function scales, and the symptom scales on the EORTC QLQ-C30 questionnaire, and the index value and the EQ VAS on the EQ-5D-5L questionnaire will be summarized by visit for the S-588410 Group and the Observation Group, respectively.

8.10 Safety Analyses

8.10.1 Adverse Events

AEs will be classified by system organ class and preferred term using Medical Dictionary for Regulatory Activities (MedDRA) Version 16.0 or higher. Of reported AEs on the CRF, TEAEs will be used in the S-588410 Group and AEs will be used in the Observation Group for safety analyses. The definition of TEAE is described in Section [7.6.11](#).

For the S-588410 Group, the number and the percentage of patients who experienced TEAEs will be summarized. For the overall summary of TEAE, the number and the percentage of patients who have experienced death, serious TEAEs, Grade 3 or higher TEAEs, and TEAEs that lead to withdrawal of study drug will also be summarized. The number of those TEAEs, which are counted by cases reported, will also be presented. ADRs will be summarized by the same as TEAE category of overall summary. For the summary of TEAE by system organ class and preferred term, the number of patients who have experienced TEAEs will be presented for the S-588410 Group with the percent of patients. The summary by severity and the summary by outcome will be presented by system organ class and preferred term.

For the S-588410 Group, the number and the percentage of patients who experienced local reaction-related AEs as the injection sites will be summarized. In a similar fashion, eosinophilic pneumonia-related AEs, flulike symptoms-related AEs, and anaphylactic reaction-related AEs will be tabulated, respectively.

For the Observation Group, the number and the percentage of patients who experienced AEs will be summarized. For the overall summary of AE, the number of patients who have experienced death, SAEs will be presented with the percent of patients who have experienced their AEs. The number of those AEs, which are counted by cases reported, will also be presented. For the summary of AE by system organ class and preferred term, the number of patients who have experienced AEs will be presented for the Observation group with the percent of patients. The summary by severity will be presented by system organ class and preferred term.

All AEs including AEs that have presented prior to or after the first dose of the study drug will be listed.

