For the ITT population, the OS will be estimated with the Kaplan-Meier method and the median OS and the associated 90% CI will be presented for the S-588410 Group and the Observation Group, respectively.

For the ITT population, the change from baseline in the global health status, the function scales, and the symptom scales on the EORTC QLQ C30 questionnaire, and the index value and the EQ VAS on the EQ-5D-5L questionnaire will be summarized by visit for the S-588410 Group and the Observation Group, respectively.

Safety analysis:

AEs will be classified by system organ class and preferred term using Medical Dictionary for Regulatory Activities (MedDRA) Version 16.0 or higher. Of reported AEs on the case report form (CRF), Treatment-emergent adverse events (TEAEs) will be used in the S-588410 Group and AEs will be used in the Observation Group for safety analyses. TEAE is defined as AE occurring after the initial dose of the study drug.

For the S-588410 Group, the number and the percentage of patients who experienced TEAEs will be summarized. For the overall summary of TEAE, the number and the

percentage of patients who have experienced death, serious TEAEs, Grade 3 or higher TEAEs, and TEAEs that lead to withdrawal of study drug will also be summarized. The number of those TEAEs, which are counted by cases reported, will also be presented. Adverse drug reactions (ADRs) will be summarized by the same TEAE category as overall summary.

For the summary of TEAE coded by system organ class and preferred term, the number of patients who have experienced TEAEs will be presented for the S-588410 Group with the percentage of patients. The summary by severity and the summary by outcome will be presented by system organ class and preferred term.

The number and the percentage of patients who experienced local reaction-related AEs at the injection sites will be summarized. In a similar fashion, eosinophilic pneumonia-related AEs, flulike symptoms-related AEs, and anaphylactic reaction-related AEs will be tabulated, respectively.

Study Duration:

Study duration for individual patients: 108 weeks (Screening Period, 4 weeks; Treatment Period, 104 weeks)

Planned Overall Study Period: from February 2014 to October 2018

Date of Original: 25 December 2013

TABLE OF CONTENTS

SYNOPSIS.....	2
TABLE OF CONTENTS	9
LIST OF IN-TEXT TABLES	12
LIST OF ABBREVIATIONS AND DEFINITIONS OF TERMS	13
1. INTRODUCTION	15
1.1 Bladder Cancer	15
1.2 Cancer Peptide Vaccine.....	16

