3. INVESTIGATIONAL PLAN

3.1 Overall Study Design and Plan

The study is an open-label, multicenter study and consists of 2 study periods:

- The Screening Period is 28 days prior to enrollment. Potential patients who provided written informed consent will be screened for assessment of the eligibility in the screening period.
- The Treatment Period/Observation Period is 24 months (104 weeks) after enrollment. Eligible patients will be enrolled in the study, and assigned to S-588410 Group or Observation Group depending on the HLA-A genotype. Enrollment form will be reported via FAX.

[figure not shown]
For Japanese study sites	Sponsor's study manager: [REDACTED], Clinical Research Department, Shionogi & Co., Ltd. FAX: [REDACTED]
For EU study sites	Sponsor's medical monitor: [REDACTED] Medical Consultant Oncology, Shionogi Ltd. Fax: [REDACTED]

- HLA-A*24:02-positive patients will be enrolled in the S-588410 Group. Each patient will receive 1 mL of S-588410 emulsion, which contains 1 mg each of S-288301 (DEPDC1-derived peptide), S-288302 (MPHOSPH1-derived peptide), S-488401 (URLC10-derived peptide), S-488402 (CDCA1-derived peptide), and S-488403 (KOC1-derived peptide). S-588410 will be injected subcutaneously in the patient's inguinal, axillary, or cervical region once weekly for 12 weeks and once every 2 weeks thereafter for up to 24 months. They will undergo efficacy assessments (specific CTL measurement, anti-tumor evaluation, PFS, OS, and EORTC QLQ-C30 and EQ-5D-5L questionnaire assessment), safety assessments (injection site assessment, physical examination, vital sign assessment, electrocardiogram [ECG], Eastern Cooperative Oncology Group Performance Status [ECOG PS], laboratory tests, and adverse event [AE] monitoring), and other assessments (antigen expression testing and T-cell receptor repertoire analysis).
- HLA-A*24:02-negative patients will be enrolled in the Observation Group and will not receive the study drug. They will undergo the efficacy and safety assessments similarly to the S-588410 Group except for specific CTL measurement, and injection site assessment, and T-cell receptor repertoire analysis.

Follow-up assessments will be performed in all enrolled patients for 3 years after enrollment of the last patient. The following data will be reported to the sponsor: survival or death, date and site of progression, and date, description of, and response to subsequent therapy for the target disease (ie, bladder cancer).

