3.3 Study Duration

3.3.1 Study Duration in individual patients

The total study duration will be 108 weeks (Screening Period, 4 weeks; Treatment Period, 104 weeks).

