7.6 Adverse Events Assessments

7.6.1 Performing Adverse Events Assessments

AEs will be found by the patient's spontaneous complaint, or as a result of nonleading questions, physical examination, vital signs, or laboratory tests. AEs include any occurrences that are new in onset or aggravated in severity or frequency from the baseline condition, or abnormal results of diagnostic procedures, including laboratory test abnormalities. Medical histories which are reported at the baseline and worsen will be considered as AEs. Aggravation of target disease (eg, tumor growth and the appearance of new lesion) or any symptoms and/or signs associated with target disease (eg, cancer pain and carcinomatous pleural effusion) result in any of the outcomes such as death or life-threatening condition in Section 7.6.8.1, they must be considered as AEs and serious AEs (SAEs). Aggravations of target disease other than those above are not considered as AEs in the study because they will be evaluated as other assessments (eg, Tumor evaluation, QOL assessment, and ECOG [PS]).

The investigator or subinvestigator will assess AEs in the S-588410 Group and the Observation Group. AEs should be fully investigated and recorded in detail including onset date, date of outcome assessment (if outcome is other than not recovered or unknown), severity, seriousness with a category of seriousness, relationship with the study drug, action taken to manage the AE, and outcome of the AE in the CRF.

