7.6.2 Timing

AEs will be collected from the time of informed consent through Visit 59 (or Discontinuation). Any SAE in the S-588410 Group assessed as causally related to the study drug and ongoing at Visit 59 (or Discontinuation) will be followed until resolution, stabilization, the condition becomes chronic, or the patient is lost to follow-up. Any AEs ongoing at Visit 59 (or Discontinuation) will be followed until resolution, stabilization, the condition becomes chronic, or 30 days after Visit 59 (or Discontinuation).

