7.6.11 Treatment-Emergent Adverse Events

AEs reported after the initial dose of study drug in the S-588410 Group will be considered TEAE.

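### Adverse event tables start at the first dose for S-588410 but at informed consent for the Observation Group, and the TEAE definition differs between the synopsis and section 7.6.11

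*Protocol*

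**What the plan says.** - **Collection.** Protocol section 7.6.2: "AEs will be collected from the time of informed consent through Visit 59 (or Discontinuation". The rule is not split by group, and section 7.6.1 confirms that both are covered: "The investigator or subinvestigator will assess AEs in the S-588410 Group and the Observation Group".
- **Tabulation.** Section 8.10.1: "TEAEs will be used in the S-588410 Group and AEs will be used in the Observation Group for safety analyses". S-588410 events before the first dose appear only in the listing at the end of that section.
- **TEAE, as used by section 8.10.1.** That section refers to section 7.6.11: "AEs reported after the initial dose of study drug in the S-588410 Group will be considered TEAE". The Observation Group has no equivalent start.
- **TEAE, as given in the synopsis (safety analysis).** "TEAE is defined as AE occurring after the initial dose of the study drug".
- **Lengths.** Section 3.1: "The Screening Period is 28 days prior to enrollment". Section 3.3.1: "The total study duration will be 108 weeks (Screening Period, 4 weeks; Treatment Period, 104 weeks".
- **Safety population.** Section 8.3: "all enrolled patients in the S-588410 Group who receive at least 1 actual dose of S-588410 and all patients enrolled in the Observation Group".

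**The concern.** Read together, sections 7.6.2, 7.6.11 and 8.10.1 give the two groups different time origins. An event that begins during screening counts in the tables if the patient later enters the Observation Group, but not if the patient enters the S-588410 Group. Only the start differs; collection ends at Visit 59 or discontinuation in both.

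The extra period need not be typical of the rest. Exclusion criterion 5 allows the first dose as early as 3 weeks after prior therapy, so screening can overlap the weeks just after platinum chemotherapy. Section 1.3 says that S-588410 had not been given to humans, and section 8.1 says that tables will generally be shown by treatment group. Readers are therefore likely to set the untreated group's rates beside the S-588410 rates.

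The TEAE definition is a second, separate problem. An event that begins before the first dose and is reported after it is not a TEAE under the synopsis but is one under section 7.6.11. Two programmers could produce different S-588410 tables from the same data, each following the protocol.

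**Working it through.** **1. The plan's own figure.** Screening 4 weeks + treatment or observation 104 weeks = 108 weeks, as stated in section 3.3.1. As written, 108 weeks is also the longest Observation AE window. The S-588410 tables cover at most the 104 weeks from the first dose.

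**2. Share of extra time.** 104 weeks × 7 = 728 days, and 728 + 28 = 756 days. Screening is 28/756 = 3.7% of the Observation window.

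**3. Expected event counts.** Assume a constant AE rate, T weeks of observation after enrollment, and the full 4 weeks from consent to enrollment. The ratio of events counted to events counted from enrollment is (T + 4)/T. The protocol gives neither an AE rate nor an expected time on study, so T is varied.

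**4. Patients with at least one AE.** Suppose a share P would have an AE after enrollment. With s screening weeks counted as well, the share becomes 1 − (1 − P)^((T + s)/T). P = 50% is an assumption for illustration.

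| T (weeks) | Event ratio, s = 4 | Share with any AE, s = 4 | Share with any AE, s = 1 |
|---|---|---|---|
| 104 | 108/104 = 1.04 | 51.3% | 50.3% |
| 52 | 56/52 = 1.08 | 52.6% | 50.7% |
| 24 | 28/24 = 1.17 | 55.5% | 51.4% |
| 12 | 16/12 = 1.33 | 60.3% | 52.8% |

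For example, at T = 12 and s = 4: 1 − 0.5^(16/12) = 1 − 0.397 = 60.3%.

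**5. Which rows are plausible.** AE collection stops at discontinuation, and section 7.7 withdraws patients who need chemotherapy for their disease. Section 3.2.2 cites a median overall survival of 10.3 months after first-line chemotherapy, or 10.3 × 52/12 ≈ 45 weeks. Full 104-week observation is therefore unlikely to be typical, but the protocol does not say what is.

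**6. After the fix.** Starting the Observation tables at enrollment cuts the longest window from 108 to 104 weeks. Table 7-3 places enrollment at Visit 1, before the initial administration, so this is the closest counterpart to the first dose.

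**7. The two TEAE wordings.** Any event that occurs after the first dose is also reported after it. The reverse is false. The section 7.6.11 set therefore contains the synopsis set plus pre-dose events reported late, so its count is equal or larger. The protocol gives no basis for estimating how many events that adds.

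**The case against.** **No AE comparison is planned.** The safety objective concerns patients receiving S-588410, and the Observation Group's objective covers tumor evaluation, PFS, OS and QOL. Section 8.10.1 summarises the groups in separate paragraphs with partly different categories and no test, and allocation is by HLA-A genotype. This stands: no inference is invalidated. Descriptive rates shown by group still need a common, stated origin.

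**The direction is not established.** A reader might infer that the rule makes S-588410 look safer. The documents do not support that. The longer window raises Observation counts, but S-588410 patients attend weekly and then every 2 weeks, whereas Observation patients come about every 12 weeks after week 12 (Appendices 1 and 2). Denser visits may uncover more events under S-588410, and the report-based TEAE wording can only add to that group's counts.

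**The size is easily overstated.** At an assumed 0.5% to 2% per day, the chance of any AE in 28 days is 1 − exp(−28h), or 13% to 43%. A reader might take that as the inflation of the table. It is not. At 0.5% per day, 728 days give 1 − exp(−3.64) = 97.4% and 756 days give 1 − exp(−3.78) = 97.7%, a difference of 0.3 points. Moreover, 28 days is the stated screening length, and many patients may be enrolled sooner.

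**Screening events are limited.** Section 7.6.1 counts only events that are new or worse than baseline, so stable chemotherapy toxicity is not an AE. The safety population contains enrolled patients only, so screening deaths cannot enter. Several exclusion criteria remove patients with serious problems at enrollment. These points reduce the extra events but do not remove them.

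**The SAP could settle it.** Section 8.1 says the SAP follows this section of the protocol, and section 8.10.1 already names the event set for each group. The correction belongs in the protocol.

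**Conclusion.** The mismatch is real and nothing else in the protocol repairs it. As written, screening-period AEs enter the Observation tables and not the S-588410 tables. Relative to a common start, the effect can only be upward for Observation: about 4% more expected events at 104 weeks of observation, 8% at 52, 17% at 24 and 33% at 12. These figures assume the full 28 days of screening and a constant event rate; time on study is also assumed. A shorter screening interval makes them smaller. A higher event rate soon after chemotherapy would make them larger.

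The net direction of a side-by-side reading cannot be derived from the protocol, and no bias in favor of S-588410 has been shown. Nor are the S-588410 tables confined to time on treatment: TEAEs have no limit tied to the last dose.

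The conflict over TEAE is certain from the wording alone and does not depend on any comparison between groups. Because section 8.10.1 points to section 7.6.11, the report-based version is the one that would be applied.

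**What to change.** 1. In both the synopsis and section 7.6.11, define a TEAE as an AE with **onset** after the first dose of study drug.
2. In section 8.10.1 and the matching synopsis text, state that the Observation tables include AEs with onset on or after enrollment (Visit 1, Day 1).
3. List AEs with earlier onset separately for both groups. Collection from informed consent can stay as it is.
4. Where the tables are shown by group, add a note that the groups are not randomised and have different visit schedules. The common start does not remove that difference.

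The cost is wording and the corresponding table programming. Section 7.6.1 already requires the onset date, so no new data, visits or patients are needed, and the sample size and primary analysis are untouched.
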